10.5 Sensitivity Analyses for SVR

As sensitivity analyses, the number and percentage of subjects in the mITT-GT and mITT-GT-VF populations achieving SVR₁₂ will be summarized by GT (GT5 and GT6) across treatment arms, along with two-sided 95% CIs using the normal approximation to the binomial distribution and the Wilson's score method.

A different CI will be calculated for the primary endpoint of SVR₁₂ based on the ITT population as a sensitivity analysis. If the number of SVR₁₂ non-responders is ≥ 5 , then the two-sided 95% CI using Wilson's score method will be calculated. If the number of SVR₁₂ non-responders is < 5 , the two-sided 95% CI using the normal approximation to the binomial distribution will be calculated.

Listings of subjects excluded from the mITT-GT and mITT-GT-VF populations will be provided, as applicable.

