8.0 Statistical Methods and Determination of Sample Size

8.1 Statistical and Analytical Plans

The primary analysis will occur after all subjects have completed the PT Week 12 Visit or prematurely discontinued treatment. The data for the primary analysis will be locked after data cleaning. Data after PT Week 12 will be added to a new version of the database which will be cleaned and locked at the end of the study.

SAS[®] (SAS Institute, Inc., Cary, NC) for the UNIX operating system will be used for all analyses. All confidence intervals will be two-sided with an alpha level of 0.05.

Descriptive statistics will be provided, such as the number of observations (N), mean, and standard deviation (SD) for continuous variables and counts and percentages for discrete variables.

Safety, and demographic analyses will be performed on all subjects who receive at least one dose of study drug.

Efficacy analyses will be performed on the intention-to-treat (ITT) population defined as all enrolled subjects who receive at least one dose of study drug, unless otherwise specified.

Sensitivity analyses of the primary efficacy endpoint, when applicable, will be performed on the intention-to-treat population modified to exclude subjects not of GT5, 6 according to phylogenetic analyses (mITT-GT), and on the mITT-GT population further modified to exclude subjects who did not achieve SVR₁₂ for reasons other than virologic failure (mITT-GT-VF).

No data will be imputed for any efficacy or safety analysis except for analyses of SVR endpoints (HCV RNA data). HCV RNA values will be selected for the analyses of all SVR endpoints (e.g., SVR₄, SVR₁₂, and SVR₂₄) based on defined visit windows. A backward imputation method will be used to impute missing responses for SVR analyses.

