8.1.2.3 Sensitivity Analysis

As sensitivity analyses, the number and percentage of subjects in the mITT-GT and mITT-GT-VF populations achieving SVR₁₂, as applicable, will be summarized along with

a two-sided 95% confidence interval using the normal approximation and a two-sided 95% confidence interval using the Wilson's score method.

The two-sided 95% confidence interval using Wilson's score method will also be calculated as a sensitivity analysis for the primary endpoint of SVR₁₂ based on ITT population.

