4.2 Design Diagram

Study M16-126 is a Phase 3b, open-label, nonrandomized, multicenter study to evaluate the efficacy and safety of GLE/PIB in adults with chronic HCV GT5 or 6 infection, without cirrhosis or with compensated cirrhosis, who are either treatment-naïve or treatment-experienced with IFN or pegIFN with or without RBV or treatment-experienced with SOF plus RBV with or without pegIFN.

The study will enroll approximately 80 eligible subjects. A minimum of 15 GT5 and 30 GT6 subjects and up to approximately 16 subjects with compensated cirrhosis (regardless of GT) will be enrolled. Each subject will be assigned to one of two treatment arms based on their cirrhosis status. Non-cirrhotic subjects (Arm A) will be treated with GLE/PIB 300 mg/120 mg once daily for 8 weeks, while subjects with compensated cirrhosis (Arm B) will be treated with GLE/PIB 300 mg/120 mg once daily for 12 weeks.

Scheduled visits for subjects in the Treatment Period consist of Day 1 and Weeks 1, 2, 4, and 8 for all subjects and an additional Week 12 visit for subjects in Arm B. Subjects who complete or prematurely discontinue study drug will be followed for 24 weeks. During the Post-Treatment Period, all subjects will have visits at Post-Treatment Weeks 4, 12, and 24.

Figure 1. Study Schematic

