4.3 Sample Size

In Phase 2 and 3 studies, Study M14-868 and Study M14-172, GT 5 and 6 subjects were enrolled to demonstrate the pangenotypic efficacy of GLE/PIB across GT1-6 for the label

approved treatment duration. The current study, Study M16-126, serves to generate additional efficacy and safety data from GT 5 and 6 subjects in a wider geographic region. Therefore, no formal hypothesis will be tested in this study. The sample size of this study is determined based on operational considerations of enrolling subjects with less common HCV genotypes.

If the observed SVR₁₂ rate in this study is 97% among the expected 30 GT5 and 50 GT6 subjects, then the expected 95% confidence intervals (CIs) for the SVR₁₂ rate using the Wilson's score method¹ are (84.2%, 99.3%) and (88.2%, 99.1%), respectively, based on the Wilson's score CIs calculated for 1000 simulated samples of 30 GT5 and 50 GT6 subjects with an SVR₁₂ rate of 97% using SAS[®]. The Wilson's score method is expected to be used instead of the normal approximation method because the number of SVR₁₂ non-responders is expected to be less than 5 (see Section 10.3).

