10.3 Primary Efficacy Analysis

The primary efficacy endpoint is SVR₁₂ (HCV RNA < LLOQ 12 weeks after the last actual dose of study drug) in the ITT population. The number and percentage of subjects achieving SVR₁₂ will be summarized by GT (GT5 and GT6) across treatment arms. The number and percentage of subjects achieving SVR₁₂ will be calculated along with a two-sided 95% CI using the normal approximation to the binomial distribution, unless the number of SVR₁₂ non-responders is less than 5, where the Wilson's score method¹ will be used to calculate the CI instead.

A summary of reasons for SVR₁₂ non-response (e.g., on-treatment virologic failure, relapse, other) will be provided. A listing of subjects who do not achieve SVR₁₂ by reason for non-response will also be provided.

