10.7 Additional Efficacy Analyses

As additional analyses, the analyses of SVR₁₂ (as described in Section 10.3) and on-treatment virologic failure and Relapse₁₂ (as described in Section 10.4) in the ITT population and the sensitivity analyses of SVR₁₂ in the mITT-GT and mITT-GT-VF populations (as described in Section 10.5) will be performed for the overall population

across treatment arms and genotypes. For the SVR₁₂ endpoints, two-sided 95% CIs using both the normal approximation to the binomial distribution and the Wilson's score method will be calculated. For the other endpoints, only the two-sided 95% CI using Wilson's score method will be calculated.

The following additional efficacy endpoints will be summarized and analyzed for the ITT population, by GT (GT5 and GT6) across treatment arms and overall:

- The percentage of subjects with HCV RNA < LLOQ at each post-baseline visit in the Treatment Period (using data as observed);
- The percentage of subjects with SVR₄;
- The percentage of subjects with SVR₂₄;
- The percentage of subjects who relapsed after achieving SVR₁₂ (**Relapse₂₄**).
- The percentage of subjects with virologic failure through Post-Treatment Week 12 (i.e., the SVR₁₂ non-responders due to **on-treatment virologic failure** or **Relapse₁₂**)

For each of the above endpoints, a two-sided 95% CI using Wilson's score method will be calculated along with the number and percentage of subjects. Imputations for missing data will be performed as described in Section 6.3 for all the additional endpoints listed above except the first one.

For the overall ITT population and by GT, a summary of the subjects who completed treatment and relapsed (defined as **Relapse_{overall}**) will be prepared displaying the number and percentage of subjects relapsing overall and by the SVR visit window where the first relapse occurred (within the SVR₄, SVR₁₂, SVR₂₄ windows or after SVR₂₄ window), including the subject number and the SVR visit window corresponding to the first occurrence of relapse. A similar summary will be prepared for subjects who prematurely discontinued treatment and relapsed after having HCV RNA < LLOQ at their Final Treatment Visit.

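### With fewer than 5 SVR12 non-responders, the case the SAP expects, SAP 10.5 makes the ITT sensitivity interval by genotype a Wald interval, which breaks down there and cannot check the primary Wilson interval

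*SAP*

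**What the plan says.** SAP 10.3 and Protocol 8.1.2.1 use the normal approximation for the primary ITT interval, "unless the number of SVR₁₂ non-responders is less than 5, where the Wilson's score method" replaces it. Protocol 1.1 gives the reason: a regulatory authority asked for Wilson at high SVR12 rates below 100%.

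SAP 10.5 gives the ITT sensitivity analysis whichever method the primary analysis did not use. With 5 or more non-responders, "then the two-sided 95% CI using Wilson's score method will be calculated". With fewer than 5, "the two-sided 95% CI using the normal approximation to the binomial distribution will be calculated". SAP 4.3 expects the second case. The SAP states no truncation at 100% and no special rule for an observed rate of 100%.

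Protocol 8.1.2.3 differs: "The two-sided 95% confidence interval using Wilson's score method will also be calculated as a sensitivity analysis for the primary endpoint", with no condition on the number of failures. SAP 12.1 lists the new expected intervals that follow from the updated primary rule, but not the change to the sensitivity interval.

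For mITT-GT and mITT-GT-VF, both Protocol 8.1.2.3 and SAP 10.5 call for Wald and Wilson together. SAP 10.7 does the same for overall SVR12: "two-sided 95% CIs using both the normal approximation to the binomial distribution and the Wilson's score method will be calculated".

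**The concern.** A sensitivity interval should be a credible second answer to the same question. Here the method removed from the primary analysis for small failure counts returns as the check on that analysis, in exactly those counts. Near 100% the Wald interval either collapses to a point or runs past 100%, and its lower limit is too high. A reader comparing it with the primary Wilson interval would see a narrower, higher interval and could take that as reassurance. Since the study tests no hypothesis, the intervals are its only formal statement of uncertainty about efficacy, so a supporting interval should be one that can be interpreted.

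**Working it through.** **Inputs.** "All confidence intervals will be two-sided with an alpha level of 0.05" (Protocol 8.1), so z = 1.960. Planning case: "If the observed SVR₁₂ rate in this study is 97% among the expected 30 GT5 and 50 GT6 subjects" (SAP 4.3). Lower range of sizes: "A minimum of 15 GT5 and 30 GT6 subjects" (SAP 4.2). The count of non-responders is taken within each genotype, as in the primary analysis.

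**Reproducing the plan's figures.** Wilson limits averaged over Binomial(n, 0.97) are 84.1–99.2% (n=30) and 88.2–99.1% (n=50). SAP 4.3 gives 84.2–99.3% and 88.2–99.1% from 1000 simulated samples, which agrees within simulation error. The Wald half-width z√(0.97×0.03/n) is 0.061 and 0.047, as in Protocol 8.2. Added to 97%, those half-widths already give upper limits of 103.1% and 101.7%.

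**When Wald fails.** With f failures and p = (n−f)/n, the interval is p ± z√(p(1−p)/n). At f = 0 the width is zero. For f ≥ 1 the upper limit exceeds 100% when f < z²n/(n+z²). With z² = 3.84 this bound is 3.84×30/33.84 = 3.4 at n=30 and 3.84×50/53.84 = 3.6 at n=50, so one to three failures are affected at both sizes.

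| Failures | n=30 Wald | n=30 Wilson | n=50 Wald | n=50 Wilson |
|---|---|---|---|---|
| 0 | 100–100% | 88.6–100% | 100–100% | 92.9–100% |
| 1 | 90.2–103.1% | 83.3–99.4% | 94.1–101.9% | 89.5–99.7% |
| 2 | 84.4–102.3% | 78.7–98.2% | 90.6–101.4% | 86.5–98.9% |
| 3 | 79.3–100.7% | 74.4–96.5% | 87.4–100.6% | 83.8–97.9% |
| 4 | 74.5–98.8% | 70.3–94.7% | 84.5–99.5% | 81.2–96.9% |

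**How often, at a true 97%** (exact binomial):

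| | n=30 | n=50 |
|---|---|---|
| 0 failures, zero width | 40.1% | 21.8% |
| 1–3 failures, upper limit above 100% | 58.7% | 71.9% |
| Either | 98.8% | 93.7% |
| 4 failures, proper Wald interval | 1.0% | 4.6% |
| 5 or more, SAP switches to Wilson | 0.2% | 1.7% |

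**Sensitivity to the rate.** The probability of 0 to 3 failures is 93.9% (n=30) and 76.0% (n=50) at a true 95%, and 64.7% and 25.0% at 90%. At the GT5 minimum of n=15 and 97% it is 99.9%.

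**Coverage at 97%.** At n=30 the Wald interval contains 97% for 1 to 4 failures: 58.7 + 1.0 = 59.7%. At n=50 it does so for 1 to 6 failures: 71.9 + 4.6 + 1.3 + 0.3 = 78.1%. That is Wald used throughout. Under the SAP rule, 5 or more failures go to Wilson, whose upper limit at 5 failures (95.7% at n=50) is already below 97%, so the n=50 figure becomes 71.9 + 4.6 = 76.5%; n=30 is unchanged. For comparison, Wilson covers 94.0% and 93.7%, and Clopper-Pearson 98.8% and 98.3%.

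**Overall population, n=80, at 97%.** Zero width has probability 8.7% and Wald coverage is about 91%.

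**The case against.** The strongest reply is that nothing depends on this interval. The primary interval is Wilson whenever failures are below 5, there is no hypothesis test, and a Wilson interval is reported for every SVR12 estimate concerned. This stands, and it limits the point to the quality of a supporting analysis.

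A second reply is that the change from the protocol has a sensible origin. Once Amendment 1 made Wilson primary for few failures, the Protocol 8.1.2.3 text would print the same interval twice; SAP 10.5 sets out to give a different one. That also stands. It explains the rule, but not the choice of Wald as the alternative or the missing entry in SAP 12.1.

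A third reply is that an upper limit above 100% is a display matter that truncation would cure. Truncation would cure only that. The zero width at no failures would remain, and so would the high lower limit: 90.2% for 29/30 under Wald against 83.3% under Wilson. Most of the coverage loss at 97% comes from the zero-failure outcome, so coverage and zero width are largely the same defect seen twice.

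A reader might infer that the mITT-GT-VF result would be shown with no uncertainty at all. The documents do not support that: Wilson is required beside Wald there, so 30/30 would also carry 88.6–100%. Nor is that pair an SAP departure, since the protocol specifies it. A reader might also carry the by-genotype coverage figures over to the overall population, but at n=80 coverage is about 91%.

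**Conclusion.** The point holds for the ITT sensitivity interval by genotype. In the branch the SAP expects, four of the five possible failure counts (0 to 3) give a zero-width interval or one that passes 100%; only 4 failures gives a proper Wald interval. By probability this is 98.8% (GT5) and 93.7% (GT6) at a true 97%. It rests on the planned sizes, on no truncation rule, and on 97%, which the documents offer as an illustrative observed rate and not as a hypothesis; the affected share falls as the true rate falls, most clearly for GT6.

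It would be too strong to say that the primary result is compromised or that Wald intervals stand alone in the report. The primary interval is sound in these cases and Wilson is always available. What fails is the purpose of the sensitivity analysis, together with a change from the protocol that SAP 12.1 does not record.

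**What to change.** In SAP 10.5, use the Clopper-Pearson exact interval for the ITT sensitivity analysis when there are fewer than 5 non-responders, and keep Wilson when there are 5 or more. Returning to the protocol's Wilson interval would only duplicate the primary one when failures are below 5. List the change from Protocol 8.1.2.3 in SAP 12.1.

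For mITT-GT, mITT-GT-VF and overall SVR12 (SAP 10.5 and 10.7), state that interpretation rests on the Wilson interval already planned. With fewer than 5 non-responders, either replace the Wald interval or state that it is not interpreted.

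The cost is a few lines of SAP text and a small programming change. The exact interval is slightly wider: for 29/30 it is 82.8–99.9%, against 83.3–99.4% for Wilson. No protocol amendment is needed for this alone.

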10.6 Efficacy Subgroup Analysis

The percentage of subjects with SVR₁₂ in the ITT population will be presented along with two-sided 95% Wilson score CIs by GT (GT5 and GT6) across treatment arms, and overall, for the following subgroups:

- Prior HCV treatment history (naïve or experienced);

- For treatment-experienced subjects, type of previous regimen (IFN- or SOF-based);
- IL28B genotype (CC or non-CC);
- Sex (male or female);
- Age (< 65 or ≥ 65 years) and (< 75 or ≥ 75 years);
- Race (White, Black/African-American, Asian, or other) and (Asian or non-Asian);
- Baseline BMI (< 30 or ≥ 30 kg/m²);
- Baseline HCV RNA level (< 1,000,000 or ≥ 1,000,000 IU/mL, < 2,000,000 or ≥ 2,000,000 IU/mL);
- Baseline fibrosis stage (F0 – F1, F2, F3, or F4);
- Baseline cirrhosis status (yes/no);
- Baseline platelet count (< 90 or ≥ 90 × 10⁹/L);
- Baseline albumin (< 35 or ≥ 35 g/L);
- Baseline creatinine clearance (< 60, ≥ 60 to < 90, ≥ 90 mL/min);
- Baseline eGFR (< 90 or ≥ 90 mL/min/1.73 m²);
- History of diabetes (yes/no);
- Baseline metabolic syndrome (yes/no);
- Use of stable opiate substitution (yes/no);
- Former injection drug user (yes, within last 12 months; yes, more than 12 months ago; or no)

The 2-sided 95% Wilson score confidence interval will be produced if there are at least 10 subjects in the subgroup.

10.7 Additional Efficacy Analyses

As additional analyses, the analyses of SVR₁₂ (as described in Section 10.3) and on-treatment virologic failure and Relapse₁₂ (as described in Section 10.4) in the ITT population and the sensitivity analyses of SVR₁₂ in the mITT-GT and mITT-GT-VF populations (as described in Section 10.5) will be performed for the overall population

across treatment arms and genotypes. For the SVR₁₂ endpoints, two-sided 95% CIs using both the normal approximation to the binomial distribution and the Wilson's score method will be calculated. For the other endpoints, only the two-sided 95% CI using Wilson's score method will be calculated.

The following additional efficacy endpoints will be summarized and analyzed for the ITT population, by GT (GT5 and GT6) across treatment arms and overall:

- The percentage of subjects with HCV RNA < LLOQ at each post-baseline visit in the Treatment Period (using data as observed);
- The percentage of subjects with SVR₄;
- The percentage of subjects with SVR₂₄;
- The percentage of subjects who relapsed after achieving SVR₁₂ (**Relapse₂₄**).
- The percentage of subjects with virologic failure through Post-Treatment Week 12 (i.e., the SVR₁₂ non-responders due to **on-treatment virologic failure** or **Relapse₁₂**)

For each of the above endpoints, a two-sided 95% CI using Wilson's score method will be calculated along with the number and percentage of subjects. Imputations for missing data will be performed as described in Section 6.3 for all the additional endpoints listed above except the first one.

For the overall ITT population and by GT, a summary of the subjects who completed treatment and relapsed (defined as **Relapse_{overall}**) will be prepared displaying the number and percentage of subjects relapsing overall and by the SVR visit window where the first relapse occurred (within the SVR₄, SVR₁₂, SVR₂₄ windows or after SVR₂₄ window), including the subject number and the SVR visit window corresponding to the first occurrence of relapse. A similar summary will be prepared for subjects who prematurely discontinued treatment and relapsed after having HCV RNA < LLOQ at their Final Treatment Visit.

The number and percentage of subjects who do not achieve SVR₂₄ will be summarized by reason for non-response (as defined in Section 10.1) for the overall ITT population and by GT. For the overall ITT population, the number and percentage of subjects who do not achieve SVR₁₂ will also be summarized by reason for non-response. Listings of the subject numbers of those who do not achieve SVR₁₂ and SVR₂₄ and the reasons for non-response will also be prepared.

The concordance between SVR₁₂ and SVR₂₄ will be assessed for the overall population (across genotype and treatment arm) by the agreement between SVR₁₂ and SVR₂₄ and the positive predictive value (PPV) and negative predictive value (NPV) of SVR₁₂ on SVR₂₄. The agreement between SVR₁₂ and SVR₂₄ is a percentage defined as the number of subjects achieving both SVR₁₂ and SVR₂₄ and the number of subjects where both SVR₁₂ and SVR₂₄ are not achieved. The PPV of SVR₁₂ on SVR₂₄ is the proportion of subjects who achieve SVR₂₄ out of all subjects who achieved SVR₁₂. The NPV of SVR₁₂ on SVR₂₄ is the proportion of subjects who do not achieve SVR₂₄ out of all subjects who did not achieve SVR₁₂. Similarly, the concordance between SVR₄ and SVR₁₂ will be summarized for the overall population.

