6.3 Missing Data Imputation

Missing Data Imputation for SVR

HCV RNA values will be selected for analysis based on the analysis windows defined in Section 6.2.

For analyses of SVR, subjects' missing visit values will have backward imputation applied, if possible. For backward imputation, if the nearest HCV RNA value after the SVR window is unquantifiable or undetectable, then it will be used to impute the HCV RNA value in the SVR window. If a subject is missing an HCV RNA value within the appropriate SVR window after performing backward imputation, then this value will be imputed with an HCV RNA value from a local laboratory if present; otherwise, the HCV RNA value will be missing. Subjects with missing HCV RNA data in the analysis window, after imputations, will be imputed as a failure.

Regardless of the imputation method described above, if a subject starts another treatment for HCV, then all HCV RNA values for this subject measured on or after the start date of the new HCV treatment will be excluded from analyses. The subject will be considered a failure for summaries of viral response at all time points after the start of the new HCV treatment.

Missing Data Imputation for Virologic Failure

If HCV RNA values from the central laboratory are missing but a local laboratory value is present in the appropriate time period, then the local laboratory value will be used to assess post-treatment relapse and on-treatment virologic failure.

Missing Data Imputation for PRO Questionnaires

The handling of missing data for PROs will be as follows. If a respondent answers at least 50% of the items in a multi-item scale of the Short Form 36 Version 2 (SF-36v2) Health Status Survey, the missing items will be imputed with the average score of the answered items in the same scale. In cases where the respondent did not answer at least

50% of the items, the score for that domain will be considered missing. The Mental and Physical Component Summary measures will not be computed if any domain is missing. Missing data handling conventions for scores related to the Work Productivity and Activity Impairment Questionnaire (WPAI) – Hepatitis C are specified in Section 10.9.

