SVR₄ = HCV RNA $<$ LLOQ in the SVR₄ window (4 weeks after the last actual dose of study drug) without any confirmed quantifiable (\geq LLOQ) post-treatment value before or during that SVR window.

SVR₁₂ = HCV RNA $<$ LLOQ in the SVR₁₂ window (12 weeks after the last actual dose of study drug) without any confirmed quantifiable (\geq LLOQ) post-treatment value before or during that SVR window.

SVR₂₄ = HCV RNA $<$ LLOQ in the SVR₂₄ window (24 weeks after the last actual dose of study drug) without any confirmed quantifiable (\geq LLOQ) post-treatment value before or during that SVR window.

Relapse₁₂ = confirmed HCV RNA \geq LLOQ between end of treatment and 12 weeks after last actual dose of study drug (up to and including the SVR₁₂ window) for a subject with HCV RNA $<$ LLOQ at Final Treatment Visit who completed treatment, excluding reinfection as described below.

Relapse₂₄ = confirmed HCV RNA \geq LLOQ within the SVR₂₄ window for a subject who achieved SVR₁₂ and has HCV RNA data available in the SVR₂₄ window, excluding reinfection.

Relapse_{overall} = confirmed HCV RNA \geq LLOQ between end of treatment and up to and including the last HCV RNA measurement collected in the Post-Treatment Period for a subject with HCV RNA $<$ LLOQ at Final Treatment Visit who completed treatment, excluding reinfection.

Virologic failure for SVR₁₂ = On-treatment virologic failure or Relapse₁₂.

Only subjects who have at least one post-treatment HCV RNA value will be included in analyses of relapse. For the analysis of relapse, completion of treatment is defined as any subject with study drug duration of 52 days or greater for Arm A, and 77 days or greater for Arm B. If the last available post-treatment value is \geq LLOQ, then the subject will be considered a relapse (i.e., will not require confirmation).

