5. Prematurely discontinued study drug with no on-treatment virologic failure (defined as any SVR₂₄ non-responder who prematurely discontinued study drug [study drug duration < 52 days for subjects in Arm A, and < 77 days for subjects in Arm B] and did not meet the **On-treatment virologic failure, HCV reinfection, Relapse₁₂, or Relapse₂₄** definitions);

6. Missing follow-up data in the SVR₂₄ window (defined as any subject who completed study drug without data in the SVR₂₄ window after applying the imputation rules and not meeting the definitions of [1], [2], [3], [4], or [5]);
7. Other (defined as any SVR₂₄ non-responder not meeting the definitions of [1] – [6]).

For the reasons for SVR₁₂ and SVR₂₄ nonresponse defined above, subjects are only to be counted in one category in the order shown above. Specifically, subjects who were SVR₁₂ or SVR₂₄ nonresponders meeting the definition of HCV reinfection will be counted in the reinfection category regardless of whether they meet the definition of prematurely discontinued study drug, Relapse₁₂ or Relapse₂₄.

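### The planned SVR12/SVR24 and SVR4/SVR12 concordance scores missing follow-up as non-response, so PPV mixes absence with relapse and reinfection, and subjects missing at both times count as agreement

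*SAP*

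**What the plan says.** The concordance paragraph of SAP 10.7 defines three measures for the overall population. For PPV it says: "The PPV of SVR₁₂ on SVR₂₄ is the proportion of subjects who achieve SVR₂₄ out of all subjects who achieved SVR₁₂". For NPV: "The NPV of SVR₁₂ on SVR₂₄ is the proportion of subjects who do not achieve SVR₂₄ out of all subjects who did not achieve SVR₁₂". Agreement is called a percentage, but it is defined only as the count achieving both endpoints together with "the number of subjects where both SVR₁₂ and SVR₂₄ are not achieved"; no denominator is given. SVR4 against SVR12 is to be handled in the same way. The paragraph says nothing about missing data.

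The missing-data rule is in SAP 6.3. A missing window is filled first from a later sample: "if the nearest HCV RNA value after the SVR window is unquantifiable or undetectable, then it will be used to impute". A local-laboratory value is tried next. After that: "Subjects with missing HCV RNA data in the analysis window, after imputations, will be imputed as a failure". SAP 10.7 applies this to SVR4 and SVR24: "Imputations for missing data will be performed as described in Section 6.3 for all the additional endpoints listed above except the first one". SAP 10.1 confirms the result by listing "Missing follow-up data in the SVR₂₄ window" among the reasons for SVR24 non-response.

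The definition of Relapse24 in SAP 10.1 takes the other approach. It applies only "for a subject who achieved SVR₁₂ and has HCV RNA data available in the SVR₂₄ window, excluding reinfection".

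**The concern.** Counting missing data as failure is conservative for a response rate, because it can only lower the rate. In a cross-classification of two endpoints it has no single direction. It moves an SVR12 responder who is absent at Week 24 into the discordant cell, and it places a subject absent at both times in the concordant-negative cell. The first lowers PPV and agreement; the second supports NPV and agreement.

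PPV is the figure a reader would use to judge whether SVR12 can stand in for SVR24. A value near 95% could be taken as evidence of late virologic failure when part or all of the shortfall is missed visits. SAP 10.7 does not ask for a missing count beside PPV or NPV, so the table alone cannot settle the question.

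**Working it through.** **Inputs.** N is about 80 (SAP 4.2). The planning SVR12 rate is 97% (SAP 4.3; Protocol 8.2). The SVR24 window is Study Drug End Days 127 to 210 (SAP Table 2). No document gives a dropout rate between Post-Treatment Weeks 12 and 24, so the number missing is assumed and shown as a range.

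**The plan's own figures.** None is stated for concordance. The 97% rate is used only for precision: 1.96 × √(0.97 × 0.03 / n) gives 0.061 for n = 30 and 0.047 for n = 50, as in Protocol 8.2.

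**Step 1: who is scored discordant.** A missed Week 24 visit is not enough. The subject must have no value in Days 127 to 210, no unquantifiable value that fills the window from after Day 210, and no local-laboratory value. Only then does SAP 6.3 make the subject an SVR24 failure.

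**Step 2: PPV.** 97% of 80 is 77.6, so take 78 SVR12 responders and 2 non-responders. Let m responders lack any usable Week 24 value and r have an observed late relapse.

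- Planned PPV = (78 − m − r) / 78
- Observed-data PPV = (78 − m − r) / (78 − m)
- Planned agreement = (78 − m − r + 2) / 80, assuming a denominator of 80 and both non-responders also failing SVR24

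With r = 0:

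| m (assumed) | Planned PPV | Observed-data PPV | Planned agreement |
|---|---|---|---|
| 0 | 78/78 = 100% | 100% | 80/80 = 100% |
| 1 | 77/78 = 98.7% | 100% | 79/80 = 98.75% |
| 2 | 76/78 = 97.4% | 100% | 78/80 = 97.5% |
| 3 | 75/78 = 96.2% | 100% | 77/80 = 96.25% |
| 4 | 74/78 = 94.9% | 100% | 76/80 = 95.0% |
| 5 | 73/78 = 93.6% | 100% | 75/80 = 93.75% |

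Each missing subject costs 1/78 = 1.3 points of PPV, the same as one late relapse. With r = 1 and m = 4, planned PPV is again 73/78 = 93.6%, identical to m = 5 with no relapse; the observed-data value is 73/74 = 98.6%.

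**Step 3: NPV.** The denominator is about 2. If both non-responders are missing at both times, planned NPV is 2/2 = 100%, while on observed data it is 0/0 and cannot be estimated. NPV is also high by construction, because a confirmed quantifiable post-treatment value up to the SVR12 window bars SVR24 as well (SAP 10.1).

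**Step 4: backward imputation.** A missing SVR12 filled from an unquantifiable Week 24 sample makes both endpoints one measurement, so agreement is automatic. The same applies to SVR4 filled from Week 12. A comparison on known status therefore needs an actual value in each window.

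For SVR4 against SVR12 the mechanism is the same, but an SVR12 gap can be filled from a Week 24 sample and an SVR4 gap from Week 12. No separate size was worked out for that pair.

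**The case against.** The strongest defence is that the concordance compares two ITT endpoints exactly as the SAP defines them, and that durability is addressed elsewhere. Relapse24 is limited to SVR12 responders with data in the SVR24 window. Relapse overall is shown by the window of first occurrence. SVR24 non-response is tabulated by reason, with missing follow-up as a category, and listed by subject. This stands, and it limits the point to one descriptive analysis. It does not make PPV itself readable. The missing-follow-up category covers only subjects who completed study drug; a subject who stopped early and has no Week 24 value goes to the premature-discontinuation category, so the reason table does not give the full missing count.

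A second objection concerns the remedy. Requiring a usable value in both windows would drop known virologic failures who did not return or who started another HCV treatment, since SAP 6.3 excludes their later values. It would also be biased if dropout were related to outcome. This stands too. It is why a known-status version should sit beside the planned one and retain established failures.

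A reader might go further and infer that PPV and NPV measure dropout instead of durability. The documents do not support that. PPV mixes missing follow-up with late relapse and reinfection, and it equals the observed-data value when nobody is missing. NPV is weak mainly because of its denominator of about 2 and the SVR24 definition. Nor does every skipped Week 24 visit count as failure, given the imputation steps that come first.

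**Conclusion.** The point holds as a limited one. SAP 6.3 and 10.7 read together score an SVR12 responder with no usable Week 24 value as discordant, and a subject missing at both times as concordant. At 78 responders of 80, each such responder lowers PPV by 1.3 points: from 100% with none missing to 93.6% with five, with no relapse at all. The range of 0 to 5 is an assumption; with complete Week 24 data the effect is nil. The missing denominator for agreement is a gap in the text however missing data are treated.

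No primary or secondary result and no sample-size statement changes. Protocol 8.1.2.5 does not list concordance among the additional endpoints, and SAP 10.7 plans no interval or test for it. This is an inexpensive improvement to one reported table.

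**What to change.** Keep the planned version in SAP 10.7 and add a second one for SVR12/SVR24 and for SVR4/SVR12:

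- Include subjects whose status is known at both times, meaning an actual HCV RNA value in each window with no backward imputation from the other window.
- Keep as non-responders those already established as virologic failures, by a confirmed quantifiable post-treatment value or on-treatment virologic failure, even if they were later re-treated or absent.
- Show the number missing at each time as a separate row and column.
- Define agreement as (both achieved + both not achieved) divided by the number of subjects included, and state that number.

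For the planned version, also say whether a missing SVR12 may be filled from a Week 24 sample obtained after the primary lock, because SAP 4.4 keeps SVR12 results unchanged in the final report.

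The cost is SAP wording and one extra table; no new data are needed. The downside is that NPV in the added version may not be estimable, in which case the table should say so.
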